6.6. Wound assessment

A visual assessment of the LN biopsy site will be conducted by the investigator before the end of the study visit to ensure adequate haemostasis and wound management. A sterile adhesive dressing will be applied to the wound. Subjects will be asked to contact the investigator for an examination if they report any signs or symptoms related to persistent pain in the biopsy area or signs or symptoms indicating infection.

6.7. Safety

Planned time points for all safety assessments are listed in the Time and Events Table (Section 6.1). Additional time points for safety tests (such as vital signs, physical exams and laboratory safety tests) may be added during the course of the study based on newly available data to ensure appropriate safety monitoring, but this will not constitute a protocol amendment. The IRB/IEC will be informed of any safety issues that require alteration of the safety monitoring scheme.

6.7.1. Adverse Events (AE) and Serious Adverse Events (SAEs)

The definitions of an AE or SAE can be found in [Appendix 3](#).

The investigator and their designees are responsible for detecting, documenting and reporting events that meet the definition of an AE or SAE.

6.7.1.1. Time period and Frequency for collecting AE and SAE information

- Any SAEs assessed as related to study participation (e.g., protocol-mandated procedures, invasive tests) will be recorded from the time a subject consents to participate in the study up to and including any follow-up contact.
- AEs will be collected from: the start of study procedures until the follow-up contact (see Section 6.7.1.3), at the time points specified in the Time and Events Table (see Section 6.1).
- Medical occurrences that begin prior to the start of study procedure but after obtaining informed consent may be recorded on the Medical History/Current Medical Conditions section of the CRF.
- All SAEs will be recorded and reported to GSK within 24 hours, as indicated in [Appendix 3](#).

- Investigators are not obligated to actively seek AEs or SAEs in former study subjects. However, if the investigator learns of any SAE, including a death, at any time after a subject has been discharged from the study, and he/she considers the event reasonably related to the study procedures or study participation, the investigator must promptly notify GSK.

NOTE: The method of recording, evaluating and assessing causality of AEs and SAEs plus procedures for completing and transmitting SAE reports to GSK are provided in [Appendix 3](#).

6.7.1.2. Method of Detecting AEs and SAEs

Care will be taken not to introduce bias when detecting AEs and/or SAEs. Open-ended and non-leading verbal questioning of the subject is the preferred method to inquire about AE occurrence. Appropriate questions include:

- “How are you feeling?”
- “Have you had any (other) medical problems since your last visit/contact?”
- “Have you taken any new medicines, other than those provided in this study, since your last visit/contact?”

6.7.1.3. Follow-up of AEs and SAEs

After the initial AE/SAE report, the investigator is required to proactively follow each subject at subsequent visits/contacts. All SAEs, and non-serious AEs of special interest (as defined in Section [11.3](#)) will be followed until resolution, until the condition stabilizes, until the event is otherwise explained, or until the subject is lost to follow-up (as defined in Section [5.4](#)). Further information on follow-up procedures is given in Section [11.3](#).

6.7.1.4. Death Events

The Death sections of the CRF will be required to be completed for all deaths.

The Death CRF is provided immediately after the occurrence or outcome of death is reported. Initial and follow-up reports regarding death must be completed within one week of when the death is reported.

6.7.1.5. Regulatory Reporting Requirements for SAEs

Prompt notification by the investigator to GSK or designee of SAEs related to study procedures (even for non- interventional post-marketing studies) is essential so that legal obligations and ethical responsibilities towards the safety of subjects (and the safety of a product under clinical investigation are met).

GSK will comply with country specific regulatory requirements relating to safety reporting to the regulatory authority, Institutional Review Board (IRB)/Independent Ethics Committee (IEC) and investigators.

Investigator safety reports are prepared for suspected unexpected serious adverse reactions according to local regulatory requirements and GSK policy and are forwarded to investigators as necessary.

An investigator who receives an investigator safety report describing a SAE(s) or other specific safety information (e.g., summary or listing of SAEs) from GSK will file it and will notify the IRB/IEC, if appropriate according to local requirements.

6.7.2. Pregnancy

- Details of all pregnancies in female subjects will be collected after the start of the study until completion of the study.
- If a pregnancy is reported then the investigator should inform GSK within 2 weeks of learning of the pregnancy and should follow the procedures outlined in Section [11.4](#).

6.7.3. Physical Exams

- A complete physical examination will include, at a minimum, assessment of the Cardiovascular, Respiratory, Gastrointestinal and Neurological systems, as well as palpation of lymph nodes and proposed puncture sites. Height and weight will also be measured and recorded.
- A proposed biopsy site review will involve palpation of lymph nodes and proposed puncture sites as well as an assessment of the skin around the area of the proposed puncture site.
- Investigators should pay special attention to clinical signs related to previous serious illnesses

6.7.4. Vital Signs

Vital signs will be measured in semi-supine position after approximately 5 minutes rest and will include temperature, systolic and diastolic blood pressure and pulse rate. These will be recorded in the CRF.

6.7.5. Clinical Safety & Other Laboratory Assessments

All protocol required laboratory assessments, as defined in [Table 1](#), must be conducted in accordance with the SRM, and Protocol Time and Events Schedule (see Section [6.1](#)). Laboratory requisition forms must be completed and samples must be clearly labelled with the subject number, protocol number, site/centre number, and visit date. Details for the preparation and shipment of samples will be provided by the laboratory and will be detailed in the SRM. Reference ranges for all safety & other parameters will be provided to the site by the laboratory responsible for the assessments.

If additional non-protocol specified laboratory assessments are performed at the institution's local laboratory and result in a change in subject management or are considered clinically significant by the investigator (e.g., SAE or AE) the results must be recorded in the CRF.

Information for appropriate processing and handling of samples to avoid duplicate and/or additional blood draws will be described in the SRM.

All study-required laboratory assessments will be performed by a central laboratory, apart from:

- Haematology, Clinical Chemistry, Routine Urinalysis and “Other Screening Tests” as described in the appropriate row of [Table 1](#) below, which will be conducted locally at each site (with the exception of auto-antibody screening which may be conducted by a central laboratory)

NOTE: Local laboratory results are only required in the event that the central laboratory results are not available in time for either a treatment and/or response evaluation to be performed. If a local sample is required it is important that the sample for central analysis is obtained at the same time. Additionally if the local laboratory results are used to make either a treatment or response evaluation, the results must be entered into the CRF.

Haematology, clinical chemistry, urinalysis and additional parameters to be tested are listed in [Table 1](#).

Table 1 Protocol Required Safety & Other Laboratory Assessments

Laboratory Assessments	Parameters			
Haematology	Platelet Count	RBC Indices:	WBC count with Differential:	
	RBC Count	MCV	Neutrophils	
	Hemoglobin	MCH	Lymphocytes	
	Hematocrit		Monocytes	
	INR (derived from Prothrombin time) and APTT		Eosinophils	
			Basophils	
Clinical Chemistry	Urea	Potassium	AST (SGOT)	Total and direct bilirubin
	Creatinine	Sodium	ALT (SGPT)	Total Protein
	Glucose ¹	Calcium	Alkaline phosphatase	Albumin
Routine Urinalysis	
 Specific gravity pH, glucose, protein, blood and ketones by dipstick Microscopic examination (if blood or protein is abnormal) 			
Other Screening Tests	
 HIV Hepatitis B (HBsAg) Hepatitis C (Hep C antibody) Alcohol and drug screen Urine hCG Pregnancy test (as needed for women of child bearing potential)² Fasted C-peptide HbA1c anti-GAD, anti-IA2, anti-ICA, anti-IAA, anti-ZnT8, anti-thyroid peroxidase, anti-tissue transglutaminase and anti-nuclear antibody 			
NOTES :	
 1. Fasted glucose at screening, non fasted glucose on Day 1. 2. Local urine testing will be standard for the protocol unless serum testing is required by local regulation or ethics committee. 			

6.8. Biomarker(s)

With the subject's consent, iLN and peripheral blood samples will be collected during this study and used for the purposes of measuring biomarkers to aid the understanding of the pathogenesis of NOT1D and/or medically related conditions. If relevant, this approach will be extended to include the identification of biomarkers associated with adverse events. A peripheral blood sample may also be used for genotyping. Further details of experimental procedures will be provided in the SRM.

Blood samples (volume up to 30 ml) and up to two fine needle aspirate passages and up to five lymph node core biopsy samples will be collected at the time point indicated in Section 6.1.

Primary endpoint: Candidate biomarkers (= absolute numbers and/or proportion of leukocyte subsets) associated with either location of cells (i.e. iLNs derived leukocytes versus peripheral blood derived cells) and/or disease-status (i.e. HV versus NOT1D subjects) may be identified by application of flow cytometry.

- Objective: To assess the frequency and phenotype of leukocyte subsets in iLN and peripheral blood in HVs and T1D subjects
 - Leukocyte subset phenotyping will be carried out on peripheral blood and iLN-derived cells by assessing expression of but not restricted to the following antigens; CD3, CD4, CD8, CD11c, CD14, CD16, CD19, CD24, CD25, CD38, CD45RA, CD56, HLA-DR and FOXP3.

Secondary endpoint: Candidate biomarkers (=absolute numbers and/or proportion of leukocyte subsets) associated with type of biopsy (core biopsy versus fine needle aspirate) may be identified by application of flow cytometry.

- Objective: To assess the frequency and phenotype of leukocyte subsets from iLN core biopsy versus iLN fine needle aspirate in HVs and T1D subjects:
 - Leukocyte subset phenotyping will be carried out on iLN-derived cells by assessing expression of but not restricted to the following antigens; CD3, CD4, CD8, CD11c, CD14, CD16, CD19, CD25, CD24, CD38, CD45RA, CD56, HLA-DR and FOXP3

Exploratory endpoints: Novel candidate biomarkers and functional analysis of iLN-derived cells and cells from peripheral blood will be assessed depending on the material available.

- Objective: To assess suppression activity of T regulatory lymphocytes from the iLN and peripheral blood in HVs and NOT1D subjects
 - T regulatory suppression analysis may be carried out by a micro suppression assay or alternative equivalent.
- Objective: To assess the frequency of cytokine-producing lymphocytes in HVs and NOT1D subjects.
 - Percentages of lymphocytes (and subsets) producing pro- and or anti-inflammatory cytokines may be identified by flow cytometry (for example, but not restricted to, Th1 and Th17 cells).
- Objective: To assess clonal expansion of T and B lymphocyte populations in HVs and NOT1D subjects
 - T and B lymphocyte clones may be assessed by TCR and BCR deep sequencing.
- Objective: To assess the gene expression fingerprint of auto-antigen specific lymphocytes in HVs and NOT1D subjects

- For analysis of autoreactive T lymphocyte function, iLN-derived lymphocytes and PBMCs may be stimulated with antigens such as GAD65 or proinsulin. Gene expression of autoreactive T lymphocytes may be analysed by RNA (Ribonucleic Acid) sequencing (and/or equivalent methodologies) of sorted T cell populations. The RNAs assayed/identified may be those involved with the pathogenesis of T1D.
- Objective: To assess the phenotype and transcriptomic fingerprint of stromal cells from iLN core biopsy samples in HVs and NOT1D subjects
 - Phenotyping of stromal cells, including but not limited to fibroblastic reticular cells, from iLN core biopsy samples may be carried out by assessing expression of, but not limited to, the following antigens: CD45, CD31, gp38, MHC II.
 - Gene expression of stromal cells, including but not limited to fibroblastic reticular cells, may be analysed by RNA sequencing (and/or equivalent methodologies)

All samples will be retained for a maximum of 15 years after the last subject completes the trial.

6.9. Genetics

Information regarding genetic research is included in [Appendix 2](#).

7. DATA MANAGEMENT

- For this study, subject data will be entered into GSK defined CRFs, transmitted electronically to GSK or designee and combined with data provided from other sources in a validated data system.
- Management of clinical data will be performed in accordance with applicable GSK standards and data cleaning procedures to ensure the integrity of the data, e.g., removing errors and inconsistencies in the data.
- Adverse events and concomitant medications terms will be coded using MedDRA (Medical Dictionary for Regulatory Activities) and an internal validated medication dictionary, GSKDrug.
- CRFs (including queries and audit trails) will be retained by GSK, and copies will be sent to the investigator to maintain as the investigator copy. Subject initials or other Personally Identifiable Information (PII) will not be collected or transmitted to GSK according to GSK policy.
- Screen failure information will be entered in to the clinical database (see also Section [5.3](#))

8. STATISTICAL CONSIDERATIONS AND DATA ANALYSES

This is a non-randomized study, without an investigational drug.

All data required for the analysis of primary, secondary and exploratory objectives will be captured in the clinical database and included in the clinical report. Further details will be provided in the RAP.

8.1. Hypotheses

This study is designed to explore the phenotype of immune cells in the iLN and peripheral blood (such as, but not restricted to PBMCS) of NOT1D subjects compared to HVs.

There are no formal hypotheses being tested due to the exploratory nature of the study. Primary comparisons of NOT1D subjects to HVs will be made using an estimation approach, providing point estimates and confidence intervals.

Secondary comparisons of biopsy methods will be made within NOT1D subjects and HVs using an estimation approach:

- iLN biopsies will be carried out by two related methods, fine-needle aspirate and core biopsy sampling:
- If sufficient numbers of cells to meet the cell number requirements of the primary endpoint are obtained by both biopsy methods, the primary endpoint analysis will be carried out independently for each biopsy method, otherwise only the biopsy method for which sufficient numbers of cells were obtained will be used for primary analysis.
- If no meaningful differences between biopsy methods are observed, material from both biopsy methods may be pooled to meet exploratory objectives 1, 2, 3 and 4. Material from fine-needle aspirate and core biopsies will **not** be pooled unless supported by the comparison described above.
- If meaningful differences in the proportion of leukocyte subsets between cells derived from each biopsy method **are** observed, then :
 - If sufficient number of core biopsy derived cells are available, these will be analysed for exploratory objectives 1, 2 and 5.
 - Fine needle aspirate derived cells will be used to meet exploratory objectives 3 and 4. If insufficient number of core biopsy derived cells are available to meet exploratory objectives 1 and 2, then fine needle aspirate derived cells may be used to meet either or both of those exploratory objectives

8.2. Sample Size Considerations

This is an exploratory study and there are no formal sample size calculations. The upper limit for sample size (n=15 per group) has been based on feasibility.

8.2.1. Sample Size Assumptions

For PBMCs, literature data was available for lymphocytes CD4+, CD8+ and regulatory T-cells in HVs using a similar gating strategy to that planned here. Computer simulation were performed to assess the expected precision of estimation of odds ratios and relative risks for a cross sectional comparison of PBMC regulatory T-cells for a range of differences between NOT1D subjects and HVs. The average precision for both PBMC estimates is expected to be within 1% of the point estimate using n=15 per group

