8.4. Key Elements of Analysis Plan

8.4.1. Primary Analyses

Descriptive statistics will be calculated for each of the primary flow cytometry cell types by group and sample type (blood / core biopsy / fine needle aspirate biopsy). The flow cytometry data for each cell type will be displayed graphically using scatter plots of cell count and % cell count versus group and/or sample type.

Generalized linear models with appropriate link functions will be used to analyze data separately for each flow cytometry cell type. Models will include terms for group, sample type, and the interaction of group with sample type. Subject will be included as a random effect term.

- For absolute cell counts, these models will estimate the mean cell count for each sample type in each group, comparing means as outlined in the primary hypothesis section.
- For proportional cell counts, these models will estimate the average odds (or relative risk) of having a particular cell type for each sample type in each group, comparing these odds (or relative risks) by estimating the ratios for the primary comparisons of interest.

All estimates will be presented with 95% confidence intervals.

Model assumptions will be checked, and modifications to the model or alternative approaches may be considered in the event of significant deviations from model assumptions.

Further details will be provided in the Reporting and Analysis Plan (RAP).

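### Protocol 8.2.1 promises blood Treg odds ratios and relative risks to within 1% at 15 per group; precision is undefined, and on the usual readings the design cannot be expected to deliver it

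*Protocol*

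**What the plan says.** Protocol 8.2 states that there is no formal sample size calculation and that "The upper limit for sample size (n=15 per group) has been based on feasibility". Section 8.2.1 then gives the protocol's one quantitative statement about what that number achieves. It says that "literature data was available for lymphocytes CD4+, CD8+ and regulatory T-cells in HVs using a similar gating strategy", that "Computer simulation were performed to assess the expected precision of estimation of odds ratios and relative risks for a cross sectional comparison" of blood regulatory T-cells "for a range of differences between NOT1D subjects and HVs", and concludes: "The average precision for both PBMC estimates is expected to be within 1% of the point estimate using n=15 per group".

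Apart from n, the section gives no number that went into the simulation: no Treg proportion, between-subject SD, cell count per subject or effect values. It does not say what precision means, or whether the simulation let subjects differ from one another. Neither version of the SAP (interim or final) supplies these items.

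Four other places bear on the meaning:
- Section 8.1: "Primary comparisons of NOT1D subjects to HVs will be made using an estimation approach, providing point estimates and confidence intervals".
- Section 8.4.1: "All estimates will be presented with 95% confidence intervals". It also plans a random effect for subject.
- Section 8.2.2 expects iLN estimates to be less precise than blood estimates because fewer cells will be available. It also says that no sensitivity analysis was done.
- Section 8.3.2 has the second interim, at 5 evaluable HVs and 5 evaluable NOT1D subjects, re-assess precision because variability is uncertain. SAP 3.1.2 repeats this in both versions.

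**The concern.** The plan is built on estimates with 95% confidence intervals, so a statistician will read precision as a standard error or an interval half-width. Section 8.2.2 points the same way, since it describes an error that grows as counts fall. On either reading, 1% for a ratio between two groups of 15 people leaves almost no room for people to differ from one another.

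What is at stake is the expectation set for readers of the protocol. This is its only figure for what 15 per group can show, and 8.2.2 describes the iLN estimates relative to it. Someone designing the possible follow-up interventional study and taking the 1% at face value would expect far tighter estimates than a study of this size usually gives.

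**Working it through.** **The plan's own figure.** It cannot be reproduced, because the inputs are missing. The check instead asks what would have to be true for 1% to hold.

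**Inputs.** n = 15 per group (protocol 8.2, 8.2.1) and a 95% level (8.4.1). The between-subject SD on the log scale, the Treg proportion (5%) and the cell count per subject (100,000) are assumptions; the documents give none of them.

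**Step 1: SD needed for 1%.** With independent subjects, SE(log ratio) = SD × √(2/15) = SD × 0.3651. The 95% half-width is t(0.975; 28) × SE, with t = 2.0484. Set each equal to ln(1.01) = 0.00995:
- SE reading: SD = 0.00995 / 0.3651 = 0.0273.
- 95% half-width reading: SD = 0.00995 / (2.0484 × 0.3651) = 0.0133 (0.0139 with z = 1.96).

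At an assumed median of 5%, logit(0.05) ± 1.96 × SD puts 95% of subjects between 4.75% and 5.26% (SE reading) or between 4.88% and 5.13% (half-width reading). This allows nothing for cell-counting error.

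**Step 2: what 15 per group gives over a range of assumed SDs.** SE as exp(SE) - 1; limits as exp(±t × SE) - 1. For example, at SD 0.20, SE = 0.0730 and t × SE = 0.1496, so the limits are +16.1/-13.9%.

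| Assumed SD (log scale) | SE of ratio | 95% limits around ratio |
|---|---|---|
| 0.05 | 1.8% | +3.8/-3.7% |
| 0.10 | 3.7% | +7.8/-7.2% |
| 0.20 | 7.6% | +16.1/-13.9% |
| 0.30 | 11.6% | +25.2/-20.1% |
| 0.40 | 15.7% | +34.9/-25.9% |

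An SE of 1% would need 51, 203 and 809 subjects per group at SD 0.05, 0.10 and 0.20. A 95% half-width of 1% would need 196, 778 and about 3,106.

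**Step 3: does the size of the difference matter?** Simulation used 20,000 runs per setting, true odds ratios 0.67 to 1.5, logit-normal subjects, a 5% proportion and 100,000 CD4+ cells per subject. At SD 0.20 it gave limits of +16.0/-13.8% for the odds ratio and +14.9 to +15.3/-13.0 to -13.3% for the relative risk. The true difference hardly changes the result.

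**Step 4: readings on which about 1% could arise.**
- *Cells treated as independent, no subject variation.* SE(log OR) = √(2 / (15 × M × p × (1-p))). At p = 5%, about 28,000 cells per subject give a 1% SE, and about 109,000 give a 1% half-width. For the relative risk the figures are about 26,000 and 98,000.
- *Signed bias of the mean simulated ratio.* exp(SD²/15) - 1 is 0.27% at SD 0.20 and 0.60% at 0.30, and reaches 1% at SD 0.386.
- *Average absolute deviation from the truth.* This is about √(2/π) × SD × 0.3651 on the log scale: about 11% at SD 0.39, and 1% only near SD 0.034. This reading does not rescue the figure.

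**The case against.** The strongest reply is that no calculation error has been demonstrated. The real inputs lie in literature data and a simulation that the documents do not reproduce, and every SD above is assumed. That is correct, and it limits the claim. The figure is unverifiable, and implausible on the usual readings; it is not a proven slip.

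A reader might go further and infer that the simulation left out between-subject variation. Section 8.2.2, which explains precision by cell number alone, makes that tempting, and step 4 shows that it would give about 1%. Such a simulation would also conflict with the subject effect planned in 8.4.1 and in section 7.1.2 of the SAP. But no passage describes the simulation model, so this is a possible cause and no more.

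A second reply is that precision may have meant bias. Signed bias would indeed stay under 1% up to an SD of about 0.39. But bias is not precision, the text does not say it was meant, and the surrounding sections use the word for random error.

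A third reply is that nothing depends on the figure. This largely stands: n is a feasibility limit, no hypothesis is tested, the second interim re-assesses precision, and stopping early under 8.2.3 relies on accrued data. The final SAP also records in the past tense (section 2.1) that most exploratory objectives were not evaluated, so it was written with study experience in hand, and observed intervals would supersede a planning figure. These facts keep the point small, but they do not make the sentence right.

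**Conclusion.** The sentence is wrong as written: it states a precision that the design does not have on the usual readings. With subjects as the unit, 1% requires a log-scale SD of at most about 0.027 (SE) or 0.013 (95% half-width). An assumed SD as small as 0.05 already misses it on both. Over the assumed range of 0.05 to 0.40, the shortfall is roughly twofold to sixteenfold on the SE (1.8% to 15.7% against 1%). The conclusion rests on independent subjects, a common SD in both groups and one of the two usual meanings of precision. It does not depend on which SD in that range is chosen.

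A reader might also infer that 15 per group is too few, or that the study's results will carry false precision. The documents support neither. The sample size was not derived from the 1%, and the reported intervals will come from a mixed model with a subject effect. The damage is confined to one planning statement, so the severity is minor.

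**What to change.** The simplest change is to delete the 1% sentence from 8.2.1. If a planning figure is wanted, replace it with the expected 95% limits for the NOT1D:HV ratio, from the simulation re-run with a between-subject variance component and its inputs stated. For example:

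> *Simulations assuming a blood Treg proportion of [p] of CD4+ cells, a between-subject log-odds SD of [value, source], [m] CD4+ cells per subject and true odds ratios of [range] give expected 95% limits of +[x]/-[y]% around the odds ratio and +[x]/-[y]% around the relative risk at 15 per group.*

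If no SD can be sourced, show the limits over a range labelled as assumed, such as +8/-7% at SD 0.10, +16/-14% at 0.20 and +35/-26% at 0.40. If the 1% was the signed bias of the mean simulated ratio, call it bias and do not present it as precision.

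The cost is one sentence and, unless it is simply deleted, one re-run of an existing simulation. The sample size stays as it is. The only downside is a less favourable stated figure.
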